It is long been established that mindfulness practices like meditation and yoga are associated with positive mental health outcomes.^{8,9} In addition, mindfulness practices are known to support interpersonal relationships.¹⁰ In the workplace, mindfulness practice improves communication, builds a sense of shared goals leading to greater productivity and retention, and helps to decrease burnout.^{11,12} Furthermore, mindfulness practices foster resilience. Mindfulness practices are also associated with improved physiologic function including autonomic nervous system (ANS) function.¹³ Peripheral ANS activity, including cardiac vagal activity (indexed by heart rate variability [HRV]), regulates dynamic fine-tuning of feedback loops between emotion-related brain circuitry and the heart.¹⁴ HRV is known to be a robust biomarker of health, wellness, stress, and the ability to self-regulate.¹⁵ By instructing individuals in MBIs homeostasis in brain-heart feedback loops is promoted leading to autonomic stability.¹⁶ Given the potential impact of MBI to promote individual and workplace wellness, investigation of this intervention to improve wellness in academic faculty and staff is critical.

3. Study Design

3.1. Describe the study design (e.g., observational; randomized placebo-controlled clinical trial, etc.)

This study is a minimal-risk, single site, quasi-experimental study.

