The UNM CON currently employs 71 faculty and 71 staff and the HSC has additional nurse faculty and staff. We will employ a quasi-experimental design to assess feasibility, acceptability, and preliminary efficacy of MBIs (meditation; yoga) to increase a sense of belonging and connectedness in academic nursing faculty and staff. Using convenience sampling we will recruit and enroll 60 participants in to two study groups: 1) mindfulness mediation and 2) yoga. Interested study participants will be contacted by study staff and screened to determine study eligibility (See Attachment A). The screener is approximately 1-page in length and takes approximately 5 minutes to complete. The screener includes queries related to inclusion and exclusion criteria. Participants will also complete an Exercise Participation Screening (see Attachment B).¹⁷

Pre-data collection:

We will assign 15 individuals to each condition. Across both conditions, all participants will participate in one baseline assessment/training session, 6 weeks of MBIs (participants will be required to attend 2 sessions per week), and a post-intervention assessment session. Following screening for inclusion/exclusion criteria, eligible participants will complete the BEING Mindful Exercise participation screening. Eligible participants will provide informed consent.

After informed consent is obtained, research staff will allocate individuals to meditation vs yoga on 1:1 basis. If an individual is unable to participate in the yoga arm based on the BEING Mindful Exercise participation screening, they will be assigned to meditation and the next two participants will be assigned to yoga.

All participants will be given an anonymous study ID number once they are enrolled in the study. The only link between the study ID number and any identifier will be stored in a secure N:\Research-Studies network drive, in a folder to which only the investigators will have access. Any link between the study ID and identifiers will be destroyed when data analysis is complete.

Once we have enrolled 30 participants we will waitlist individuals for a second six-week intervention session after the completion of the first session. This will result in a possible enrollment 60 individuals.

12.3. For studies that collect existing or prospective data, describe the source of information, whether collected prospective or retrospectively.

Data collection:

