Participants who express interest and meet inclusion criteria will meet with the PI or trained research personnel to review the study protocol, including risks and benefits. Participants will be asked to read and sign the informed consent (Attachment C) and HIPPA agreement following the procedure described in Section 25 – Consent Procedure.

Baseline Assessment session: During the baseline assessment session, participants will be administered a structured questionnaire with a research team member via the secure REDCap system. Baseline self-report questionnaires will be completed: 1) Sense of Belonging Scale (SBS); 2) Mindfulness Attention Awareness Scale (MASS) 15-item; 3) Generalized Anxiety Disorder-7 (GAD-7); 4) NIH toolbox measure of perceived stress

Sample Descriptors: Sociodemographic characteristics (age, sex, physical ability, staff vs faculty, years in profession, years employment at HSC, previous mindfulness practice) will be assessed at the baseline session.

Assessment of belonging: Belonging will be assessed using the 8-item Sense of Belonging Scale (SBS). The SBS measures the sense of belongingness or feelings of acceptance and inclusion in a community experienced by an individual.²¹ The SBS was developed to be adapted to specific contexts.²¹ Using the method described by Mellinger and Park (2023), we adapted the scale to be specific to UNM HSC nurse faculty and staff. Response categories range from 1 (*Strongly disagree*) to 5 (*strongly agree*). Responses are summed and the mean is calculated with higher scores corresponding to a stronger sense of belonging.²² The SBS-8 demonstrated high levels of reliability with a Cronbach's alpha coefficient of .96.²¹

Assessment of mindfulness: *Trait mindfulness:* Trait mindfulness will be assessed using the 15-item Mindfulness Attention Awareness Scale (MAAS).²³ The MAAS was designed to assess core characteristics of mindfulness. The MAAS has demonstrated consistent reliability with Cronbach's alpha coefficients ranging from .80 to .90 in undergraduate, community, and nationally sampled adult populations.²³

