Physiologic measures: inter-beat-interval will be collected via a Garmin Vivosmart5® device. This device has been shown to produce reliable heart rate data with the mean absolute percentage error below the designated acceptable 10% threshold.³¹ Each participant will receive training for use of the sensor and written instructions will be provided for future reference. Participants will wear the device on their non-dominant hand in their daily environment every day for six weeks. Daily reminders to wear the device and to check the battery level will be delivered via the mEMA to increase compliance with the protocol.

HRV outcome measures: Garmin Vivosmart5® uses optical technology in which a series of lights emitted by photoplethysmography (PPG) sensors against the skin illuminate capillaries to detect changes in blood volume and providing heart rate data in real time.³¹ Raw data is collected from the device and sent to the phone via Bluetooth. Using the pulse to pulse (P-P) interval, inter-beat-interval (IBI) is derived via Ilumivu software. HR epochs of five-minute intervals immediately preceding and corresponding to each mEMA survey will be selected for analysis. Time and frequency domain analysis will be performed by Ilumivu using proprietary software. **Time Domain measures:** Time domain measures are based on the time difference between easily detectable QRS complexes.

Using PPG technology, these measures are derived from the P-P interval (distance in milliseconds between each P). Simple time domain measures (standard deviation of P-P interval, mean HR) will be calculated. Frequency domain measures estimate frequency spectrum. The general bands are low frequency (LF; 0.04–0.15 Hz) and high frequency (HF; 0.15–0.40 Hz). Low frequency measures, high frequency measures, and LF/HF ratio of HRV will be computed.³²

Long-term HRV, 24 hour time windows, will be determined by dividing the 24 hour time period into consecutive 5 minute epochs and averaging the individual values of the HRV metrics to obtain the mean of the value within the 24 hour time window.^{32,33} Five-minute heart rate epochs immediately following completion of each mEMA survey will also be selected for analysis.^{20,34} Between subject variability, in which relatively stable variation is compared between individuals, and within-subject (WS) variability, in which variation within the same individual across time will be examined.

12.4. Indicate what study activities happen when and where.

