Aim 1: To assess precision of estimates, 95% confidence intervals will be calculated for rates of recruitment into study, retention to end of study, and participants completing all training sessions. Overall adherence will also be described by calculating the mean and standard deviation of the number of completed training sessions per participant. Qualitative Analyses: Qualitative descriptive analysis⁴⁰ will be used to create a comprehensive summary of the acceptability of the MBI to participants. Deductive analysis will be used to determine common themes related to acceptability in the domains of affective attitude, burden, ethicality, intervention coherence, opportunity costs, perceived effectiveness, and self-efficacy.⁴¹ Interview responses will be reviewed by two members of the research team to identify themes. Themes and preliminary interpretations will be regularly presented to the larger research team to resolve any discrepancies or disagreements and check for alternative interpretations.

Aim 2: Participant characteristics and baseline survey responses will be described using means and standard deviations (SD) for continuous variables and number (percentage) for categorical variables. Continuous intervention outcomes will be described using means and standard deviations and, due to sample size, difference scores from baseline for intervention outcomes will be compared between groups using non-parametric statistical tests. Cohen's d, as a descriptive statistic, will be used as an effect size measure to quantify the extent of within group and between group differences in means over time.⁴² Long-term HRV (time domain and frequency domain measures derived for each 5 minute epoch within a 24 hour period will be averaged) measures will be compared between meditation and yoga groups by t-test. EMA and HRV data will be merged into a single dataset, matching upon timestamp.

Five-minute heart rate epochs immediately following completion of each mEMA survey will be selected for analysis.^{20,34}

13.2. Provide a power analysis, if applicable.

14. Provisions to Monitor the Data to Ensure the Safety of Subjects

This section is required when research involves more than Minimal Risk to subjects. Describe:

N/A – The PI believes this study constitutes no more than minimal risk for potential participants. Therefore, a Data and Safety Monitoring Plan is not required.

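### For the four questionnaires listed before and after treatment, section 13.1 plans only an unadjusted change-score test and no interval; a baseline-adjusted difference with a 95% CI should be reported beside it

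*Combined protocol and SAP*

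**What the plan says.** Section 13.1, Aim 2, gives the sample size as its reason for the choice of test and states that "difference scores from baseline for intervention outcomes will be compared between groups using non-parametric statistical tests". The test is not named; a two-sample rank test is the natural reading. Cohen's d is added as a descriptive effect size. No baseline covariate appears anywhere in the plan, and 95% confidence intervals are planned only for the Aim 1 rates. The opening of 13.1 says that the study should supply estimates for the power analysis of a later grant application.

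The baseline list in sections 12.3 and 12.5 begins "Baseline self-report questionnaires will be completed: 1) Sense of Belonging Scale (SBS" and goes on to the 15-item mindfulness scale (MAAS), GAD-7 and perceived stress. The post-intervention list in 12.5 names the same four. The Copenhagen Burnout Inventory is described in 12.3 but is in neither list.

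On design, section 3.1 says "This study is a minimal-risk, single site, quasi-experimental study". Section 12.2 says "We will assign 15 individuals to each condition" and, after consent, "research staff will allocate individuals to meditation vs yoga on 1:1 basis". For anyone who cannot do yoga, "they will be assigned to meditation and the next two participants will be assigned to yoga". Randomisation is not mentioned.

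Heart rate variability (HRV) is handled separately: long-term "measures will be compared between meditation and yoga groups by t-test", with no difference score stated.

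**The concern.** Subtracting the baseline score fixes its coefficient at 1. When the baseline-to-follow-up correlation is moderate, that over-corrects chance differences between the arms and adds noise that a fitted coefficient would remove. A small sample is a reason for care about the reference distribution of the test. It is not a reason to prefer subtraction to adjustment.

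What is at stake is the usefulness of the between-arm result. A p-value and a descriptive Cohen's d do not show how uncertain the difference is, and a later power calculation needs exactly that. The data for a sharper estimate with an interval are already planned for the four listed questionnaires.

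**Working it through.** **The plan's own figure.** There is no precision or power figure to reproduce. Section 5.3 gives 30 participants by citing pilot-study recommendations and a medium effect, and 13.2 (power analysis) is blank. For scale only, assume a standardised difference of 0.5 and two-sided 5%. Then 80% power needs 63 per arm; 15 per arm gives about 28% and 30 per arm about 49% (normal approximation). The 30 is a pilot convention.

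**Inputs from the documents.** 15 per arm per session (12.2), so N = 30; about 30 per arm, N = 60, if both sessions fill (5.2).

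**Assumed, because not given.** SD = 1 at both times; rho from 0.3 to 0.95; arms comparable at baseline for the precision results.

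**Precision formulas.**
- Per-person variance of the change score: 2·SD²·(1 − rho).
- Per-person residual variance after baseline adjustment: SD²·(1 − rho²).
- Ratio: (1 − rho²) / [2(1 − rho)] = (1 + rho)/2.
- Cost of estimating the slope: multiply by (N − 3)/(N − 4). At N = 30 this is 27/26 = 1.038.
- Relative CI width: square root of the adjusted ratio, times t(N − 3)/t(N − 2) at the 97.5% point.

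Example at rho 0.5, N = 30: ratio 0.75 × 1.038 = 0.779; relative width 0.884, or about 12% narrower.

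| rho | (1+rho)/2 | ratio at N = 30 | CI narrower, N = 30 | CI narrower, N = 60 |
|---|---|---|---|---|
| 0.3 | 0.65 | 0.675 | 18% | 19% |
| 0.5 | 0.75 | 0.779 | 12% | 13% |
| 0.7 | 0.85 | 0.883 | 6% | 7% |
| 0.9 | 0.95 | 0.987 | 0.5% | 1.6% |
| 0.95 | 0.975 | 1.012 | 0.8% wider | 0.3% |

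The N = 60 column leaves out the session covariate.

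**Power, like with like.** A parametric adjusted model should not be credited with the gain from leaving ranks. Simulating 4,000 trials per setting (normal data, 0.5 SD difference) gives:

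| Setting | Mann-Whitney on change | t-test on change | Adjusted linear model |
|---|---|---|---|
| 15 per arm, rho 0.8 | 50.5% | 54.3% | 57.7% |
| 30 per arm, rho 0.8 | 82.2% | 84.6% | 86.9% |

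At 15 per arm the total gain is 57.7 − 50.5 = 7.2 points, of which 54.3 − 50.5 = 3.8 come from leaving ranks. At rho 0.9 and 15 per arm the t-test on change and the adjusted model are level (84.2% and 83.9%). At rho 0.4 to 0.6 most of the gain does come from adjustment.

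**Bias if the arms differ systematically.** Assume a true baseline gap of 0.3 SD and no treatment effect.
- If the gap is stable over time, the change score is unbiased and the adjusted estimate is off by 0.3 × (1 − rho): 0.15 SD at rho 0.5, 0.09 SD at rho 0.7.
- If follow-up depends on the baseline score alone, the adjusted estimate is unbiased and the change score is off by the same amount in the other direction.

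Simulation (20,000 runs per setting, 15 per arm) agrees: 0.145 and −0.151 at rho 0.5; 0.090 and −0.093 at rho 0.7.

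**The case against.** The strongest case against is that the precision result assumes arms that are exchangeable at baseline, which these documents do not establish. The design is called quasi-experimental, no sequence or concealment is described, and the one stated departure from 1:1 allocation is health-related while the outcomes include stress and anxiety. Choosing between change score and adjustment is then partly a choice between untestable assumptions about bias. This stands, and it is why the adjusted estimate belongs beside the planned analysis and not in its place. It does not favour the change score by default, because the possible bias is equal and opposite for the two methods. Participants do not choose their arm, and the stated rule uses no outcome score. Excluding yoga-ineligible people addresses the known diversion only, not any discretion by staff.

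It also stands that the aim is preliminary. Feasibility and acceptability are primary (7.1), the Aim 2 hypotheses concern improvement from before to after (1.1), and a rank test on change scores is a valid choice in a small pilot.

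A reader might infer several stronger things that the documents do not support:
- That adjustment is free. It uses a degree of freedom, gains almost nothing at rho 0.9, and may target a different quantity under non-random allocation.
- That it applies to every outcome. Burnout is in neither assessment list. HRV is not stated to be analysed as a difference score, and its collection is described only as "Participants will wear the device on their non-dominant hand in their daily environment every day for six weeks", with no separate pre-intervention window.
- That a chance imbalance of 0.37 SD is to be expected. √(2/15) = 0.37 is the standard deviation of the baseline difference at 15 per arm; its expected absolute size is 0.37 × √(2/π), about 0.29 SD. At 30 per arm the standard deviation is √(2/30) = 0.26.

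**Conclusion.** The point holds for belonging, MAAS, GAD-7 and perceived stress. The plan leaves out an interval for the between-arm difference and a baseline-adjusted estimate, both available from data it already lists. If the arms are comparable at baseline, the interval at N = 30 would be about 18% narrower at rho 0.3, 12% at 0.5, 6% at 0.7 and 0.5% at 0.9, with no gain above that. These sizes rest on an assumed rho, equal variances at the two times and baseline comparability; none of these is given in the documents.

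It would go too far to call the planned test an error or to say that it should be replaced. The comparison remains imprecise under either method.

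**What to change.** In section 13.1, for the four questionnaires listed at both assessments:

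- Pre-specify a linear model for the post-intervention score with arm, baseline score and session (1 or 2). Report the adjusted mean difference with its 95% CI, using a permutation p-value or a robust standard error to meet the small-sample concern.
- Report it alongside the planned non-parametric test on difference scores, and name that test.
- Repeat both analyses without people who could not have been assigned to yoga.
- State that allocation is not described as randomised, so the two results may differ because of bias as well as precision, and that the adjustment uses a degree of freedom.

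The cost is a few sentences in the plan and a few lines of code. No new data are needed.

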5.3. Provide sample size justification

The planned overall sample size of 30 is consistent with recommendations for pilot studies seeking to build evidence in the context of medium effect size differences between two groups.¹⁸

6. Study Timelines

6.1. Describe:

- *The duration of an individual subject's participation in the research*
- *The duration anticipated to enroll all subjects*
- *The expected duration for the investigators to complete the study (complete analysis)*

Participants will be enrolled until the allotted 30 participants for the first 6 weeks of the study is reached. The study is comprised of a pre-intervention assessment, followed by 6 weeks of meditation/yoga attendance (twice/week). Upon completion of the 6-week intervention, participants will complete a post intervention assessment (See Table 1.).

Table 1. Study Timeline	Months									
	1	2	3	4	5	6	7	8	9	10
Prepare research and data management tools.		→								
Session 1										
Recruitment		→								
Intervention		→	→							
Data Collection		→	→							
Preliminary Data Analyses				→						
Session 2										
Intervention				→						
Data Collection				→						
Analyses					→					
Prepare R01 proposal										→
Dissemination										→

7. Study Endpoints: Primary endpoint(s) are typically efficacy measures that address the main research question. Secondary endpoints are generally not sufficient to influence decision-making alone, but may support the claim of efficacy by demonstrating additional effects or by supporting a causal mechanism.

7.1. *Describe the primary and secondary study endpoints.*

Primary outcomes of interest of this study include the feasibility and acceptability of mindfulness-based interventions (MBI) (Aim 1). We will also examine the preliminary effect of these interventions on psychosocial outcomes (primary: sense of belonging; secondary: burnout, stress) and physiologic outcomes (HRV) (Aim 2).

7.2. *Describe any primary or secondary safety endpoints.*

This is a minimal risk study.

7.3. *Describe any exploratory endpoints.*

N/A There are no anticipated exploratory endpoints.

8. Research Setting

8.1. *Describe the sites or locations where your research team will conduct the research.*

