Description of Intervention Delivery

These guidelines detail the procedures used to conduct Mindful Meditation or Yoga sessions.

We will employ a quasi-experimental design to assess feasibility, acceptability, and preliminary efficacy of MBIs (meditation; yoga) to increase a sense of belonging and connectedness in academic nursing faculty and staff. We will assign 15 individuals to each condition. Across both conditions, all participants will participate in one baseline assessment/training session, 6 weeks of MBIs (participants will be required to attend 2 sessions per week), and a post-intervention assessment session. Following screening for inclusion/exclusion criteria, eligible participants will complete the **BEING Mindful** Exercise participation screening. Eligible participants will provide informed consent.

Assignment of Participants:

After informed consent is obtained, research staff will allocate individuals to meditation vs yoga on a 1:1 basis. If an individual is unable to participate in the yoga arm, they will be assigned to meditation and the next two participants will be assigned to yoga.

Retention:

To promote retention, we will reach out to participants with frequent reminders via text messages and emails.

Baseline Assessment session: During the baseline assessment session, participant characteristics will be collected. Baseline self-report questionnaires will be completed: 1) Sense of Belonging Scale (SBS); 2) Mindfulness Attention Awareness Scale (MASS) 15-item; 3) Generalized Anxiety Disorder-7 (GAD-7); 4) NIH toolbox measure of perceived stress.

Intervention Delivery:

The meditation and yoga interventions are 6-week protocols. We will offer meditation sessions 4 times per week and yoga sessions 4 times per week. We will require participants to attend two sessions per week. Attendance will be tracked via the Ilumivu platform. Participants will be requested to log attendance at each session via the app.

The meditation intervention will be led by [name] and [name]. Meditation is a practice of mental exercises designed to increase focus and cultivate a desire to relieve suffering in self and other.^{35,36} The practice dates back millennia to Buddhist and Hindu sages, but more recent work focuses on stress.³⁷ More recently, the term mindfulness has been used which means awareness, attention, and remembering.³⁷ Many religious traditions have a form of meditation based practice. This study will focus

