For each yoga class, the instructor will lead the student through a series of yoga poses. Class will begin with centering and breathwork (pranayama) for 5-10 minutes. This will be followed by a series of warm-up poses (~5-10 minutes). After the warm-up sequence, students will flow through traditional sun salutations (~10-15 minutes). This will be followed by a series of standing poses (~ 15 minutes). Students will then be guided to flow through a series of cool-down poses on the floor (~10 minutes). Class will conclude with traditional Savasana during which affirmations or meditation are provided (~5-10 minutes).

Treatment fidelity:

Delivery: Standard treatment manuals and checklists have been developed. To ensure that the interventions are delivered as intended, yoga instructors will complete standardized checklists after each in-person session.³⁹ In addition, we will select one yoga session every 2 weeks for rating by trained research personnel. The PI and interventionists will meet to discuss results and problem solve. We will track participant's completion of study components using summary sheets for each visit. Participants will log attendance at intervention sessions using the mEMA app.

Post-intervention session: During the post-intervention assessment session, participants will be administered a structured questionnaire with a research team member via the secure REDCap system. Self-report questionnaires will be completed: 1) Sense of Belonging Scale (SBS); 2) Mindfulness Attention Awareness Scale (MASS) 15-item; 3) Generalized Anxiety Disorder-7 (GAD-7); 4) NIH toolbox measure of perceived stress. Participants will complete semi-structured (See Attachment G) interviews to help us collect data pertaining to the MBIs and delivery preferences. Interview responses will be transcribed in the REDCap system. These data will be used to adjust the content and format of the intervention based on feedback from participants who are our intended users.

13. Data Analysis

13.1. Describe the data analysis plan, including any statistical procedures.

Consistent with the scope of pilot projects, the proposed study will allow us to examine barriers to successful completion of the study, evaluation of acceptability of methods to participants, and estimates for future power analysis for a subsequent NIH R01 application. Numerical and graphical summaries will be computed for all measurements.

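### Section 13.1 plans uncorrected Cohen's d with no stated standardising SD and no pre-post correlation, so effect sizes passed to the R01 may be slightly inflated or misread in either direction

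*Combined protocol and SAP*

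**What the plan says.** Section 13.1 opens by listing what the pilot is for, including "estimates for future power analysis for a subsequent NIH R01 application". Under Aim 2 it describes continuous outcomes by means and SDs, and compares change from baseline between meditation and yoga with non-parametric tests. It then adds that Cohen's d, which it labels descriptive, "will be used as an effect size measure to quantify the extent of within group and between group differences in means over time". A reference is cited for d, but the text gives no formula, does not say which SD is the divisor, and mentions neither a small-sample correction nor the pre-post correlation.

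On size, sections 12.2 and 12.5 state "We will assign 15 individuals to each condition". Section 5.2 allows a second wave: "This will result in a possible enrollment 60 individuals". With 1:1 allocation that is 15 per arm after one wave and 30 per arm after both. Section 5.3 calls 30 overall adequate for pilots "seeking to build evidence in the context of medium effect size differences between two groups" and attaches no number to medium. Section 13.2, the power analysis, is unanswered.

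**The concern.** Two separate matters are involved.

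**Small-sample bias.** The sample SD in the denominator makes Cohen's d too large on average. The effect is systematic and has a standard correction. The size of the bias depends on the degrees of freedom of that SD, so it differs between the within-group and between-group versions.

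**Undefined standardiser.** Mean change may be divided by the SD of change or by a raw-score SD such as the baseline SD. Both are commonly called Cohen's d, yet they are different quantities linked by the pre-post correlation. The ambiguity also touches the between-group d, because the groups are compared on change scores that could be scaled either way.

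What is at stake is the use of the pilot for R01 planning. Section 13.1 names no other effect-size measure. The Aim 2 hypotheses in section 1.1 are about improvement from before to after, so the within-group d is a natural figure to quote. A reader of the report who does not know the divisor cannot tell which sample-size formula the d belongs in.

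**Working it through.** **The plan's own figure.** Section 5.3 gives 30 overall by reference to pilot-study recommendations. No alpha, power or numeric effect is given, so there is nothing to reproduce.

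**Inputs.** From the documents: 15 per arm (one wave) and 30 per arm (both waves). Assumed, because the documents do not give them: true d = 0.5 for a medium effect, two-sided alpha 0.05, 80% power, no dropout, normal data, and r from 0.2 to 0.8.

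**Reference sample size.** n per arm = 2(1.96 + 0.8416)² / d² = 15.70 / 0.25 = 62.8, so 63.

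**Step 1: bias.** The exact factor is J(df) = Γ(df/2) / [√(df/2) Γ((df−1)/2)], and the expected value of d is the true value divided by J. With the SD of change, the within-group d has df = n − 1. The between-group d with a pooled SD has df = 2n − 2. A sample size computed from the inflated d is J² times the right one.

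| d | df | J | Bias in d (1/J − 1) | N ratio (J²) | n per arm | Actual power |
|---|---|---|---|---|---|---|
| Within, n = 15 | 14 | 0.9453 | +5.8% | 0.894 | 57 | 76.1% |
| Within, n = 30 | 29 | 0.9739 | +2.7% | 0.948 | 60 | 78.2% |
| Between, 15 per arm | 28 | 0.9729 | +2.8% | 0.947 | 60 | 78.2% |
| Between, 30 per arm | 58 | 0.9870 | +1.3% | 0.974 | 62 | 79.5% |

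Simulation with 200,000 runs and a true value of 0.5 gave mean d of 0.530, 0.514, 0.515 and 0.507 in the same order, which agrees. The follow-on N is too small by 1 − J², about 3% to 11%.

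**Step 2: standardiser.** With equal pre and post SDs, SD of change = SD × √(2(1 − r)). So d on the SD of change = raw-SD d / √(2(1 − r)). The last two columns show what happens if a true raw-SD d of 0.5 is reported on the SD of change and then used as a raw-SD two-group effect.

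| Assumed r | Multiplier | d on SD of change | n per arm (63 is right) | Actual power |
|---|---|---|---|---|
| 0.2 | 0.79 | 0.395 | 101 | 94% |
| 0.5 | 1.00 | 0.500 | 63 | 80% |
| 0.7 | 1.29 | 0.645 | 38 | 59% |
| 0.8 | 1.58 | 0.791 | 26 | 44% |

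The error is nil at r = 0.5, oversizes below it and undersizes above it.

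**Step 3: scale against sampling error.** For an observed between-group d of 0.5 at 15 per arm, SE = √(2/15 + 0.25/60) = 0.371, so the approximate 95% interval is 0.5 ± 1.96 × 0.371, or −0.23 to 1.23. The bias in Step 1 is small beside this.

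**The case against.** The strongest reply is that d is labelled descriptive and that section 13.1 never names it, let alone the within-group version, as the R01 input. This stands as far as it goes. The link to the R01 is an inference from two statements in the same section.

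A reader might infer that the R01 will come out much too small. The documents do not support that. Bias alone costs between 0.5 and 4 percentage points of power. The large shortfalls in Step 2 need an extra misstep that nobody has planned, namely using a change-SD d as a raw-SD two-group d, together with a correlation well above 0.5. No correlation is given.

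A reader might also infer that the damage could not be undone. That is wrong too. Section 13.1 already promises means and SDs for the outcomes and numerical summaries of all measurements. Among participants with both assessments, mean change over baseline SD follows from these without r. The team also holds the raw data, and section 16 keeps records for at least six years.

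Nor can the baseline SD be called the only right divisor. If the R01 compares change scores, the SD of change is legitimate for the between-group effect. Finally, the cited reference may define the formula. It is not among the documents, so one can say only that the visible text states no standardiser.

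What remains after all this is that the divisor is unlabelled, a known bias is left uncorrected, and the correlation needed to move between designs is not on the reporting list.

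**Conclusion.** The point holds as a minor one. Uncorrected d overstates the effect by 1.3% to 5.8% at the planned sizes, and a follow-on N taken from it would be about 3% to 11% too small. These figures assume normal data and full retention. The missing label is the more consequential gap because the two readings of d differ by a factor of 0.79 to 1.58 over r = 0.2 to 0.8. That is a risk of misreading in either direction, not a predicted shortfall, and it rests on assumed correlations and equal pre and post SDs. Nothing here affects the Aim 1 feasibility results or the planned non-parametric comparisons.

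**What to change.** In section 13.1, Aim 2:

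- Replace Cohen's d with Hedges' g, using the degrees of freedom of the SD actually chosen.
- Label the standardiser for each contrast, baseline SD or SD of change, before results are seen.
- For each outcome report the mean change, baseline SD, post SD, SD of change and pre-post correlation, so that R01 inputs can be converted to whichever analysis the R01 uses.

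This takes one or two sentences and no new data. The cost is that reported effects shrink by the factor J, that is by 1.3% to 5.5% (1 − 0.9870 to 1 − 0.9453).
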